5.6 Concomitant Medications

All patients will be required to be administered 800 mg of ibuprofen (or equipotent and equivalent alternative NSAID) prior to administration of birinapant on Day 1 and Day 8 as prophylaxis for possible events of cranial nerve palsy associated with the administration of birinapant. Patients with a history of peptic ulcer disease or gastritis will receive proton pump inhibitor for prophylaxis.

5.6.1 Restricted and prohibited medications

Patients are prohibited from receiving the following therapies during screening and the treatment phase (dose-escalation and dose-expansion) of this study:

- Antineoplastic systemic chemotherapy or biological, immune- or chemotherapy not specified in this protocol;
- Granulocyte-macrophage colony-stimulating factor (GM-CSF)
- Investigational agents other than pembrolizumab and birinapant;
- Radiation therapy
 - Radiation therapy to a symptomatic solitary lesion or to the brain may be considered on an exceptional case by case basis after consultation with Sponsor's Medical Monitor. The patient must have clear measurable disease outside the radiated field. Administration of palliative radiation therapy will be considered clinical progression for the purposes of determining progression.
- Live vaccines within 30 days before the first dose of trial treatment and while participating in the study. Examples of live vaccines include, but are not limited to, the following: measles, mumps, rubella, chicken pox, yellow fever, rabies, BCG, and typhoid (oral) vaccine. Seasonal influenza vaccines for injection are generally killed virus vaccines and are allowed. However, intranasal influenza vaccines (e.g., Flu-Mist®) are live attenuated vaccines, and are not allowed.
- Systemic glucocorticoids for any purpose other than to modulate symptoms from adverse event of suspected immunologic etiology. The use of physiologic doses of corticosteroids may be approved after consultation with the Sponsor's Medical Monitor.
 - Inhaled steroids are allowed for management of asthma.
- Anti-TNF agents are excluded while on study treatment and must be discontinued prior to Cycle 1 Day 1 for a period of 5 half-lives. Examples include:
 - Infliximab (Remicade®)
 - Entanercept (Enbrel®)
 - Adalimumab (Humira®)
 - Certolizumab (Cimzia®)
 - Golimumab (Simponi®)

Patients who, in the assessment by the Investigator, require the use of any of the aforementioned treatments for clinical management should be removed from the study. Patients may receive other medications that the Investigator deems to be medically necessary.

Based on *in vitro* studies, birinapant is a weak-to-moderate inhibitor of CYP3A4. Co-administration of medications that are substrates for CYP3A4 may result in an increase in their systemic exposures. Therefore, drugs with a narrow therapeutic index (e.g. alfentanil, cyclosporine, sirolimus, tacrolimus, cisapride, pimozide, fentanyl, quinidine, ergotamine, dihydroergotamine, astemizole, terfenadine) should be avoided. Birinapant is also an inhibitor of P-glycoprotein (P-gp), therefore digoxin should be used with caution. Birinapant is a substrate for the hepatic uptake transporter OATP1B3 and medications that are OATP1B3 inhibitors (e.g. cyclosporine, rifampicin, lopinavir, ritonavir) should be avoided.

Because there is a potential for interaction of birinapant with other concomitantly administered drugs through the cytochrome P450 system and transporters such as P-gp and OATP1B3, the case report form must capture the concurrent use of all other drugs, over-the-counter medications, or alternative therapies. The Investigator should be alerted if the patient is taking any agent known to affect or has the potential to affect selected CYP450 isoenzymes, P-gp or OATP1B3.

Medications or vaccinations specifically prohibited in the exclusion criteria are not allowed during the ongoing study. If there is a clinical indication for any medication or vaccination specifically prohibited during the study, discontinuation from study treatment or vaccination may be required. The Investigator should discuss any questions regarding this with the Sponsor's Medical Monitor. The final decision on any supportive therapy or vaccination rests with the Investigator and/or the patient's primary physician. However, the decision to continue the patient on study treatment or vaccination schedule requires the mutual agreement of the Investigator, the Sponsor and the patient.

All treatments that the Investigator considers necessary for a patient's welfare may be administered at the discretion of the Investigator in keeping with the community standards of medical care.

All concomitant medication will be recorded on the CRF including all prescription, over-the-counter (OTC) medication, herbal supplements, and IV medications and fluids. Details regarding the generic name, reason for use, dose, route, and frequency of all prescription medications, OTC medications, or alternative therapies taken within 14 days before administration of first study dose and through 7 days after the last study-drug dose will be recorded.

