4.2.3 Definition of Efficacy Endpoints

All patients will have a tumor measurement after cycle 3 (week 9) and subsequently after every third cycle. Measures will be assessed through RECIST 1.1 until whichever of the following occurs first:

- Site-assessed disease progression is documented
- The start of new anti-cancer treatment
- Withdrawal of consent
- Death
- The end of the study

After progression, measures will subsequently be analyzed through iRECIST as an exploratory endpoint.

The outcome of a tumor measurement for RECIST 1.1 is a categorization into one of the following categories:

- CR – Complete Response
- PR – Partial Response
- SD – Stable Disease
- PD – Progressive Disease
- Non-CR/Non-PD
- Not Evaluable

For iRECIST, a tumor measurement is categorized into one of the following:

- iCR
- iPR
- iSD
- iUPD
- iCPD
- Non-iCR/Non-iPD
- Not Evaluable

Note that RECIST 1.1 and iRECIST is equivalent until Progressive Disease (PD).

There will be two RECIST 1.1 and iRECIST categorizations, one made in the clinic and one made by an independent radiologist at MEDIAN Technologies. The categorization by the independent radiologist is the one that will be used in the analyses detailed in this SAP. The categorizations at the clinic will be reported descriptively as pure explorative purpose.

A tumour measurement may consist of scans conducted at different days (during the visit window) but there will be only one date associated to the categorization for each visit. That date will be set by the independent radiologist and will be the date used in the derivation of the time to event endpoints below. The overall process for image receipt, review and reporting conducted by MEDIAN Technologies is detailed in the Imaging Review Charter -01, dated 7 February 2018.

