4.2.3.1 Overall response (and ORR) assessed through RECIST 1.1

The primary endpoint in the dose expansion phase is the overall response assessed through RECIST v.1.1 until response or progression. A patient with a best overall response of either CP or PR is defined as a patient with an overall response according to RECIST 1.1. A tumor measurement categorized as CP or PR needs a confirmed response of either CP or PR at least 4 weeks after the initial response assessment to be classified as best overall response CP or PR. Examples of patients with an overall response are the following (observations in cycle 3 (week 9) and subsequent every 3rd cycles (9 weeks between each measurement)):

- SD, SD, PR, PR, ; SD, SD, PD (overall response as PR in cycle 9 which is confirmed in cycle 12 (9 weeks after))
- SD, SD, SD, CR, CR (overall response as CR in cycle 12)

Example of patients with no overall response as assessed through RECIST 1.1:

- SD, SD, SD, SD, SD, SD, SD, SD, SD
- SD, PD(iUPD), iSD, iSD, iCPD
- SD, PD(iUPD), iSD, iSD
- SD, SD, PR, SD, SD, PD (PR in cycle 9 is not confirmed)
- SD, PD(iUPD), iPR, iSD, iSD (no overall response according to RECIST 1.1)

The overall response rate (ORR) is defined as the proportion of patients that are classified as overall responders assessed through RECIST 1.1 as described above.

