4.2.3.2 Progression Free Survival (PFS)

The PFS is defined as the length of time from the start of treatment the patient lives and does not progress (PD as assessed by RECIST 1.1). Patients who do not die or progress will be censored at the date “last known to be alive”, i.e. the latest date of contact with the patient based on all collected evaluation dates.

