4.2.3.5 Duration of response

Duration of response will be calculated as the length of time from the first date of confirmed CR/PR to the date of death or the date of first documented tumor progression (PD), whichever is earlier, using RECIST v1.1. Patients who remain alive and do not progress are censored on the date of their last tumor assessment. Response duration is only evaluated in patients with an overall response of CR or PR.

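### The SAP definitions of PFS and duration of response omit the protocol's rule that palliative radiotherapy is progression, and its effect on ORR is undefined

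*Protocol*

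**What the plan says.** Protocol 5.6.1 lists radiotherapy among the prohibited treatments and then makes an exception: "Radiation therapy to a symptomatic solitary lesion or to the brain may be considered on an exceptional case by case basis", after consultation with the medical monitor and provided that measurable disease remains outside the field. It adds: "Administration of palliative radiation therapy will be considered clinical progression for the purposes of determining progression".

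The SAP defines the endpoints without that rule:

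- **PFS (4.2.3.2)** is the time that "the patient lives and does not progress (PD as assessed by RECIST 1.1"). Otherwise, "Patients who do not die or progress will be censored at the date" the patient was last known to be alive.
- **Duration of response (4.2.3.5)** runs to death or "the date of first documented tumor progression (PD), whichever is earlier, using RECIST v1.1". Patients who are alive without PD are censored at their last tumor assessment.
- **Overall response (4.2.3.1):** "The primary endpoint in the dose expansion phase is the overall response assessed through RECIST v.1.1 until response or progression".
- **End of RECIST 1.1 assessment (4.2.3):** assessment stops at the first of several events, including "Site-assessed disease progression is documented" and the start of new anti-cancer treatment. Protocol 9.1.3 has the same list.
- **Whose reading is analysed (4.2.3):** the independent radiologist's. The listed categories are imaging outcomes, and none stands for clinical progression.

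SAP 5.9 lists one change to the planned analysis, the handling of a different number of evaluable patients. It does not mention radiotherapy.

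**The concern.** The same patient has progressed under one rule and not under the other. The radiotherapy sentence is worded as a rule for determining progression, not only as a treatment restriction, yet the analysed imaging categories cannot register it. Where the two differ, the SAP version favours the drug, because the progression event comes later or disappears.

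The SAP does deal with later therapy elsewhere. Duration of iBOR (4.2.3.9) and duration of immune response (4.2.3.13) both censor before new anticancer therapy. PFS and RECIST duration of response have no matching rule, which looks more like an omission than a choice.

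At stake are the two secondary time endpoints. If the assessment stop rule is read as not covering radiotherapy, the count of responders in the primary endpoint is affected too.

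**Working it through.** **Step 1. Follow one patient through the definitions.** Suppose a patient without RECIST PD receives palliative radiotherapy on day R. Protocol 5.6.1 puts progression at R. The SAP outcome depends on whether RECIST assessment continues after R, which neither document settles.

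| | Assessment continues | Assessment stops |
|---|---|---|
| PFS | later PD or death | death, or censored at last known alive |
| Duration of response (responders) | later PD or death | death, or censored at last scan |
| Response first documented after R | could count | cannot be recorded |

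PFS passes over R in both columns. For duration of response, the event is delayed, or it is replaced by censoring. ORR is affected only in the left column.

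**Step 2. Reproduce the design.** With n1, n, r1 and r2 from SAP Table 4 (Protocol Table 17):

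P(reject | p) = sum over x = r1+1 to n1 of P(X1 = x | n1, p) × P(X2 ≥ r2+1−x | n−n1, p)

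For colorectal cancer under the null, this is the sum over x = 1 to 13 of P(X1 = x | 13, 0.05) × P(X2 ≥ 4−x | 14, 0.05) = 0.0416.

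| Cohort | n1, n, r1, r2 | Null / target ORR | Type I error | Power |
|---|---|---|---|---|
| Colorectal | 13, 27, 0, 3 | 5% / 20% | 0.0416 | 0.801 |
| Ovarian | 16, 26, 1, 4 | 7% / 25% | 0.0306 | 0.803 |
| Cervical | 15, 25, 1, 5 | 10% / 30% | 0.0328 | 0.802 |

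The stated 0.05 (as an upper bound) and 0.80 hold. They stand unchanged if responses after radiotherapy are not counted.

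**Step 3. ORR, only if assessment continues.** The documents give no radiotherapy rate, so any added response probability under the null is an assumption. Replacing the null rate p0 by p0 + d in the formula gives:

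| Assumed d | Colorectal | Ovarian | Cervical |
|---|---|---|---|
| 1 point | 0.072 | 0.050 | 0.049 |
| 2 points | 0.111 | 0.076 | 0.070 |
| 3 points | 0.159 | 0.107 | 0.095 |

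These figures show how sensitive a small trial is. They do not estimate what would happen here.

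**Step 4. PFS, if assessment continues.** Assumptions: exponential PFS with true median m and rate λ = ln 2 / m; a share s of patients whose first progression is radiotherapy; RECIST PD found g months later, with g = 9/4.345 = 2.07 or 18/4.345 = 4.14. The observed median M solves

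- (1−s)·exp(−λM) + s = 0.5 if M ≤ g
- exp(−λM)·[(1−s) + s·exp(λg)] = 0.5 if M > g

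Take m = 1.9 months, the pembrolizumab ovarian PFS in Protocol 1.5.2, so λ = 0.3648. With s = 0.05, exp(−λM) = 0.45/0.95 = 0.474 and M = 2.05. For s between 0.05 and 0.20, M lies between 2.05 and about 2.7. With an assumed m of 4.0 months, M lies between 4.1 and 5.1. The documents fix neither s nor g.

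**The case against.** A reader might infer that the SAP lets responses after radiotherapy count towards the primary endpoint. The documents do not support this. The stop rule in SAP 4.2.3 and Protocol 9.1.3 ends RECIST 1.1 assessment at site-assessed progression or new anti-cancer treatment. A treatment that the protocol calls clinical progression fits the first of these naturally. The case is undefined rather than wrongly decided.

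The further inference that shrinkage in an irradiated lesion would be credited to study drug also meets safeguards. The exception is narrow and requires measurable disease outside the field. Protocol 5.6.1 also says that patients needing the listed treatments should leave the study. A partial response needs a 30% fall in the target-lesion sum (Protocol Table 9) and confirmation at least 4 weeks later (SAP 4.2.3.1). The Imaging Review Charter, which is not among the documents, may say how irradiated lesions are read.

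Nor does duration of response simply keep accruing. If scans stop and the patient stays alive, it is censored at the last scan.

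It can also be said that the SAP follows the protocol. Protocol 3.4.2 specifies RECIST 1.1 for these endpoints, and the PD criteria in Protocol 9.1.2 contain no clinical progression. This stands: the conflict lies first within the protocol, and the SAP inherits it. Radiographic-only PFS is a defensible choice. It is not defensible to leave two rules standing without saying which governs the analysis.

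The SAP does look beyond imaging in places. Death is an event, and SAP 5.2.2 treats some early deaths and adverse-event discontinuations before assessment as progression. Neither covers radiotherapy.

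**Conclusion.** The conflict is real for PFS and RECIST duration of response. Followed as written, the SAP delays or loses a progression event that Protocol 5.6.1 defines, in the favourable direction. For ORR the finding is only that the case is undefined. One miscredited response would be 1 of the 4 needed in the colorectal cohort, but that fraction carries no probability and is not an effect size.

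The practical effect is expected to be small. Radiotherapy is exceptional, the documents give no rate, and PFS and duration of response are descriptive secondary endpoints without inference (SAP 5.4.4). The stated alpha and power are not in error. The shifts in steps 3 and 4 rest wholly on assumed rates and delays. This is a low-severity point that is worth settling before database lock.

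**What to change.** - **SAP 4.2.3.2 and 4.2.3.5:** count the date of palliative radiotherapy as a progression event, in line with Protocol 5.6.1, and report radiographic-only PFS as a sensitivity analysis. Alternatively, keep the radiographic-only definition as the main analysis, declare the departure in SAP 5.9 and reconcile it with Protocol 5.6.1.
- **SAP 4.2.3:** state that palliative radiotherapy triggers the existing stop rule for RECIST 1.1 assessment, so that a response first documented after it does not count towards ORR. Align Protocol 9.1.3.
- **Data:** confirm that dates of on-study radiotherapy are captured on the CRF. SAP 4.1.5 includes therapy under concomitant medication, and Protocol 6.3.3 records the next cancer therapy, but neither names on-study palliative radiotherapy.

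The cost is a few sentences, a check of the CRF and one extra PFS table. PFS may come out slightly shorter. The change concerns the analysis only and has no bearing on whether radiotherapy is given.

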5.5 Dosing Delays/Dose Modifications

During the dose escalation phase dose modifications of birinapant will only be permitted in Cycle 2 and beyond (section 5.5.1). During the first cycle, patients are assessed for DLTs and dose modifications may not be performed.

Following the completion of the first cycle of therapy and in the dose expansion phase, if an AE is assessed as related to study drug the dosing may be modified according to the starting cohort dose by reducing the dose of birinapant according to the schema in [Section 5.5.1](#) . In the case where causality cannot be assigned to only one of the agents, the Investigator should first dose de-escalate birinapant, followed by withholding pembrolizumab if required. There will be no pembrolizumab dose reductions permitted in this study (for pembrolizumab dosing rules, see Table 6)

Adverse events (both non-serious and serious) associated with pembrolizumab exposure may represent an immunologic etiology. These AEs may occur shortly after the first dose or several months after the last dose of treatment. Pembrolizumab must be withheld for drug-related toxicities and severe or life-threatening AEs as per [Section 5.5.2](#) and [Section 5.5.3](#) for supportive care guidelines, including use of corticosteroids. Dosing interruptions are permitted in the case of medical or surgical events or logistical reasons not related to study therapy (e.g., elective surgery, unrelated medical events, patient vacation, and/or holidays). Patients should be placed back on study therapy within 3 weeks of the scheduled interruption, unless otherwise discussed with the Sponsor. The reason for interruption should be documented in the patient's study record.

If a patient experiences an AE in cycle 2 or beyond in the dose escalation phase or in the dose expansion phase of the study, the Investigator may hold birinapant for up to 14 days. On resolution of the AE (or return to baseline) birinapant may be restarted at their prior dose, or de-escalated, depending on the type and severity of the event. After a delay of > 14 days, the Investigator should consider removing the patient from the study.

5.5.1 **Dose Modifications Schema and Supportive Care Guidelines for Birinapant**

The following dose modification schemas for **birinapant** are required for selected AEs below.

Cranial Nerve Palsy	Birinapant
≤ Grade 1	No change; initiate corticosteroids ^{1,2}

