≥ Grade 2	Interrupt up to 14 days; may restart at same or one dose below initial dose received ²

¹Corticosteroids should be considered at the onset of any Grade cranial nerve palsy; the recommended dose is 1-2 mg/kg day of prednisone or prednisone-equivalent, until resolution or return to baseline.
² All patients that develop a cranial nerve palsy should have a blood sample taken to assess for HSV and VZV. Sites may also consider sending the patient for a MRI.

In the event of facial pain, ear pain, retro-orbital pain, or atypical or new-onset headache, it is recommended that birinapant be held, and that a course of nonsteroidal anti-inflammatory agents (NSAIDs), such as ibuprofen, be initiated, at an appropriate anti-inflammatory dose. If within 24 hours symptoms do not resolve, or worsen, or the patient develops a cranial neuropathy, a course of steroids (prednisone) should be initiated. Birinapant may be re-introduced at the resolution of the event, at the same dose or at a reduced dose (by 1 dose level) depending on the severity of the event, if the Investigator and the patient are in agreement.

Cytokine Release Syndrome	Birinapant
≤ Grade 1	Interrupt up to 14 days; initiate diphenhydramine, acetaminophen*. Restart at same dose.
Grade 2	Interrupt up to 14 days; initiate diphenhydramine, corticosteroids. Restart treatment at one dose level down
> Grade 2	Interrupt permanently; initiate diphenhydramine, corticosteroids.

*Diphenhydramine, acetaminophen or intravenous fluids should be considered at the onset of cytokine release syndrome, until resolution.

Management of Cytokine Release Syndrome (CRS): Cytokine release syndrome is defined in CTCAE v4.03 as a disorder characterized by nausea, headache, tachycardia, hypotension, rash, and shortness of breath. CRS occurs when lymphocytes (B cells, T cells, and/or natural killer cells) and/or myeloid cells (macrophages, dendritic cells, and monocytes) become activated and release inflammatory cytokines. In addition to the symptomatology defined under CTCAE, CRS may present with fever, chills, myalgias, and malaise.

Amylase or lipase Elevation	Birinapant
≤ Grade 1	No change
≥Grade 2	Interrupt up to 14 days; restart at same dose*.
*On second occurrence, after resolution or return to baseline, a dose reduction to one dose level down should be considered.	

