5.5.3 Supportive Care Guidelines for Pembrolizumab

5.5.3.1 Dose Modification and Toxicity Management Guidelines for Pembrolizumab

Dose modification and toxicity management for immune-related AEs associated with pembrolizumab

AEs associated with pembrolizumab exposure may represent an immunologic etiology. These immune-related AEs (irAEs) may occur shortly after the first dose or several months after the last dose of pembrolizumab treatment and may affect more than one body system simultaneously. Therefore, early recognition and initiation of treatment is critical to reduce complications. Based on existing clinical trial data, most irAEs were reversible and could be managed with interruptions of pembrolizumab, administration of corticosteroids and/or other supportive care. For suspected irAEs, ensure adequate evaluation to confirm etiology or exclude other causes. Additional procedures or tests such as bronchoscopy, endoscopy, skin biopsy may be included as part of the evaluation. Based on the severity of irAEs, withhold or permanently discontinue pembrolizumab and administer corticosteroids. Dose modification and toxicity management guidelines for irAEs associated with pembrolizumab are provided in [Table 6](#).

Table 6 Dose modification and toxicity management guidelines for immune-related AEs associated with pembrolizumab

General instructions: Corticosteroid taper should be initiated upon AE improving to Grade 1 or less and continue to taper over at least 4 weeks. For situations where pembrolizumab has been withheld, pembrolizumab can be resumed after AE has been reduced to Grade 1 or 0 and corticosteroid has been tapered. Pembrolizumab should be permanently discontinued if AE does not resolve within 12 weeks of last dose or corticosteroids cannot be reduced to ≤ 10 mg prednisone or equivalent per day within 12 weeks. For severe and life-threatening irAEs, IV corticosteroid should be initiated first followed by oral steroid. Other immunosuppressive treatment should be initiated if irAEs cannot be controlled by corticosteroids.				
Immune-related AEs	Toxicity grade or conditions (CTCAEv4.0)	Action taken to pembrolizumab	irAE management with corticosteroid and/or other therapies	Monitor and follow-up

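### Protocol 5.5.1 directs steroids for cranial nerve palsy and unresolved facial, ear or retro-orbital pain or headache with birinapant continued or restartable, but 5.6.1 removes such patients unless an immunologic cause is suspected

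*Protocol*

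**What the plan says.** **Protocol 5.5.1 (birinapant dose modification and supportive care).** For cranial nerve palsy of Grade 1 or lower the instruction is "No change; initiate corticosteroids". For Grade 2 or higher it is "Interrupt up to 14 days; may restart at same or one dose below initial dose received". A footnote to the same table says that corticosteroids should be considered at the onset of palsy of any grade, and recommends a prednisone-equivalent dose range. For facial, ear or retro-orbital pain, or atypical or new headache, birinapant is held and an NSAID comes first. If symptoms have not resolved within 24 hours, or worsen, or a cranial neuropathy develops, "a course of steroids (prednisone) should be initiated". Afterwards, "Birinapant may be re-introduced at the resolution of the event, at the same dose or at a reduced dose", if investigator and patient agree.

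**Protocol 5.6.1 (restricted and prohibited medications).** The prohibited list includes "Systemic glucocorticoids for any purpose other than to modulate symptoms from adverse event of suspected immunologic etiology". The text after the list says that patients who, in the investigator's assessment, "require the use of any of the aforementioned treatments for clinical management should be removed from the study". Further on, the same section says that a clinical need for a prohibited medication may require discontinuation, sends questions to the medical monitor, and makes continuation on treatment a matter of agreement between investigator, sponsor and patient.

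**The concern.** A patient with birinapant-associated palsy, or with headache that an NSAID has not settled, is given steroids because 5.5.1 says so. Under 5.5.1 that patient stays on birinapant or may go back on it. Under the removal sentence of 5.6.1 the same patient should leave, unless the event is suspected to be immunologic. Under the later text of 5.6.1 the outcome is agreed case by case.

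This is a foreseeable case. Protocol 1.6.1 reports Bell's palsy in 2 of 3 patients at 63 mg/m², which placed that dose above the maximum tolerated dose. Protocol 5.6 requires NSAID prophylaxis against palsy before every birinapant dose, and 8.4 lists palsy as an event of clinical interest.

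At stake are who stays on treatment and how comparable the discontinuation figures are. Protocol 12.6 and SAP 5.5.1 and 5.5.7 tabulate discontinuations by reason, and these tables bear on the tolerability assessment of the recommended dose. If sites follow different sections, the tables will partly reflect which section was read and not only how well the combination was tolerated.

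**Working it through.** The point sets rules against each other and the plan states no figure to reproduce, so the check is a side-by-side reading.

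1. **What 5.5.1 leads to**

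| Event | Steroids | Birinapant |
|---|---|---|
| Cranial nerve palsy, Grade 1 or lower | Started | Unchanged |
| Cranial nerve palsy, Grade 2 or higher | To be considered (footnote covers any grade) | Interrupted, restart allowed |
| Facial, ear or retro-orbital pain, new headache | Second step after an NSAID | Held, may be re-introduced |

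Continuation without interruption therefore applies only to palsy of Grade 1 or lower. In the other two rows the patient stays eligible to restart.

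2. **What 5.6.1 leads to**

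| Suspected cause | Glucocorticoid bullet | Consequence |
|---|---|---|
| Immunologic | Permitted | None under this bullet; agrees with 5.5.1 |
| Not suspected immunologic | Prohibited | Should be removed (sentence after the list), or may have to discontinue, with continuation by joint agreement (later text) |

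3. **Which row applies?** The protocol does not say. It associates palsy with birinapant (5.6) and asks for HSV and VZV testing (5.5.1), which leaves the cause open. It uses the term immunologic etiology for adverse events associated with pembrolizumab (5.5, 5.5.2, 5.5.3.1). No section classifies palsy or headache as immunologic or as not immunologic, and 5.6.1 does not refer back to 5.5.1.

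4. **Result.** If an immunologic cause is suspected, the bullet and 5.5.1 agree. If not, 5.5.1 keeps the patient on treatment or allows restart, while the removal sentence takes the patient off study. The later text of 5.6.1 differs from that removal sentence as well.

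5. **Route to the primary endpoint**
- Protocol 4.3 keeps discontinued patients in the Section 6 follow-up. Section 6.3.2 includes tumor imaging until progression, and 9.1.5 asks for the same 9-weekly schedule after treatment stops without progression.
- Protocol 9.1.3 and SAP 4.2.3 list the events that end tumor assessment. Stopping study drug is not among them.
- Protocol 12.4 and SAP 5.2.2 treat a patient as progressed only when an adverse event ends study drug before assessment, and only if there are no other data.
- What remains is the patient with no post-baseline scan. An adverse-event stop keeps that patient in the Efficacy Evaluable Population as progressed. If the stop were recorded as a prohibited-medication withdrawal instead, the patient could fall out of that population, on which SAP 5.6.1 summarizes the primary endpoint. The denominator could then depend on how the stop was coded.

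6. **Size.** A figure would need the rate of steroid-treated events at the study doses, the share of those patients removed, and the effect of removal on the chance of response. The documents give none of these. The only palsy rate is the 2 of 3 at 63 mg/m²; the highest planned dose level here is 22 mg/m², with NSAID prophylaxis.

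**The case against.** The strongest reply is that there is no conflict in practice. 5.5.1 is the event-specific instruction, and its schemas are stated to be required for selected events. Every patient also receives pembrolizumab, and the Table 6 row for other immune-related events includes neurological ones, so an investigator can reasonably suspect an immune cause and fall within the exception. Where that does not fit, 5.6.1 provides a joint decision, so removal is not automatic.

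Much of this stands. The conflict is conditional on suspected cause, and removal is not absolute. What the reply leaves unsettled is that nothing ranks 5.5.1 above 5.6.1, the judgement that decides the outcome has no criterion, and the two consequences stated within 5.6.1 differ from each other.

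Two stronger readings are tempting, and the documents do not support them.

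- **Removed patients become non-responders and power falls.** A reader might apply an assumed event rate to the target response rates. A removed patient who is still scanned can be a confirmed responder, and the deemed-progression rule is narrow. Any such calculation would also have to assume an event rate, removal of every affected patient and no response in any of them, and none of these has a source in the documents.
- **The ban reaches the treatment of pembrolizumab's immune-related events.** A reader might combine the statement that "Medications or vaccinations specifically prohibited in the exclusion criteria are not allowed during the ongoing study" with Exclusion 9 on steroids and immunosuppressants, and set it against Table 6, which says "Other immunosuppressive treatment should be initiated if irAEs cannot be controlled by corticosteroids". This is strained: Exclusion 9 concerns the 7 days before the first dose, and the glucocorticoid bullet expressly permits steroids for suspected immunologic events.

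**Conclusion.** The contradiction is real, and it is conditional. When a palsy, or a pain or headache event that has gone on to prednisone, is not suspected to be immunologic, 5.5.1 and the removal sentence of 5.6.1 give opposite dispositions, and the later text of 5.6.1 gives a third route. Because the protocol does not say how these events are to be classified, treatment continuation and discontinuation rates can differ by site.

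The effect on overall response rate is limited and cannot be quantified. It is confined to any response lost because treatment ended early, and to patients with no post-baseline scan, whose place in the denominator may depend on how the stop is coded. No loss of power should be inferred.

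The conclusion rests on a literal reading of the two sections. It assumes that some of these events will not be suspected to be immunologic, which the protocol leaves open.

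**What to change.** Reconcile three pieces of text: the cranial nerve palsy schema and the pain and headache paragraph in 5.5.1; the glucocorticoid bullet and the removal sentence in 5.6.1; and the discontinuation and joint-agreement wording later in 5.6.1. Steroid use directed by 5.5.1 should have one stated consequence for study treatment at every site, whatever the suspected cause, and 5.6.1 should cross-refer to 5.5.1 on this point. Which consequence applies is for the sponsor's medical team to decide; this review takes no position on it.

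The cost is protocol wording in one amendment, with no added procedures or patients.
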